Superior Hypogastric Blockade for Postoperative Pain

[name] [name]^{1,2}, [name], Prof³, [name], MD³, [name],
Assoc. Prof¹

1: University of Health Sciences, Kocaeli Derince Training and Research Hospital, Department of Anesthesiology and Reanimation, [name].

2: Kocaeli University School of Medicine, Department of Anatomy (PhD student), Kocaeli, Turkey.

3: University of Health Sciences, Kocaeli Derince Training and Research Hospital, Department of Gynecology and Obstetrics, [name].

Trial registration: NCT03428152

Date of the document:

Initial Release: January 30th, 2018

Study Start (Actual): February 9th, 2018

Study Completion (Actual): July 24th, 2018

Last Update: February 17th, 2019

Objectives: Total abdominal hysterectomy cause significant postoperative pain. Intraoperative superior hypogastric block may be an alternative way for acute postoperative pain relief in patients undergoing hysterectomy. This study's objective is to evaluate the effect of intraoperative superior hypogastric blocks on postoperative pain management.

Design and Subjects: Sixty female patients who underwent elective abdominal hysterectomy were included in the prospective observational cohort study. Patients were divided into two groups: Patients who had intraoperative SHP block (Hypo; n=30), and patients who did not have intraoperative SHP block (No-Hypo; n=30).

Methods: Total sample size was determined by performing a power analysis. Thirty patients were recruited for each group (CI: 95%). Patients were divided into two groups: Patients who had intraoperative SHP block (Hypo; n=30), and patients who did not have intraoperative SHP block (No-Hypo; n=30). Patients who were under the age of 18, underwent epidural catheterization and / or additional pain management modalities (transversus abdominis plane blocks, local wound site infiltration, quadratus lumborum block... etc.), operated for malignancy, operated by using a different surgical approach (i.e. vaginal hysterectomy), and prescribed preoperative antidepressants or gabapentinoids were excluded from the study.

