Duration of operation was calculated in minutes from incision to skin to skin closure. Postoperative pain assessed by 10 cm Visual Analogue Scale (VAS). Pain scores were assessed in post-anesthesia care unit (PACU), and at ward (at 1st, 6th, 12th, 24th and 48th hours). Rescue analgesic time was calculated in minutes as the time interval between the last administration of analgesic intraoperatively and the first analgesic demand in surgical ward. Postoperative nausea and vomiting, hospital stay time, total analgesic requirements of patients in PACU and in surgical ward were recorded.

Statistical Analysis: Study data were analyzed by using IBM SPSS Statistics Version 24. Mann Whitney-U test was used for numerical values which do not meet normal distribution, independent sample t test was used for body mass index, Chi-square test was used to analyze the discrete variables, and p value <0.05 was considered statistically significant. Friedman's test /post-hoc test was used to analyze the repeated measures, and Wilcoxon signed-rank test was used for paired comparison of the repeated measures. Bonferroni corrected significance was considered as p<0,0033.

Ethical Consideration: This study was approved by the Kocaeli University's Institutional Review Board (IRB KÜGOKAEK #2017/285/14.22) and written informed consent was obtained from all subjects participating in the trial. All procedures followed were in accordance with the ethical standards of the responsible committee on human experimentation and with the Helsinki Declaration of the World Medical Association.

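### The fixed 0.0033 level for the 15 paired time comparisons is valid, but Holm's step-down gives the same 5% familywise control and may find more changes

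*Combined protocol and SAP*

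**What the plan says.** The Methods give six VAS assessments: "Pain scores were assessed in post-anesthesia care unit (PACU), and at ward (at 1st, 6th, 12th, 24th and 48th hours". The Statistical Analysis paragraph describes the time-course analysis in two steps. First, "Friedman's test /post-hoc test was used to analyze the repeated measures"; then, "Wilcoxon signed-rank test was used for paired comparison of the repeated measures". The general level is "p value <0.05 was considered statistically significant", and the corrected level is "Bonferroni corrected significance was considered as p<0,0033".

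The document mentions no step-down or other sequential procedure. It does not state how many comparisons the correction covers. Nor does it say whether the paired tests are run within each group of 30 or in all 60 patients. It plans no confidence intervals for these contrasts.

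**The concern.** Every paired comparison has to pass the strictest level that the family requires, however many other pairs have already been rejected. A step-down version of the same correction is never stricter, so the fixed level may cost power with nothing gained in error control. What is at stake is the description of when pain fell over 48 hours: a pair with a p value somewhat above 0.0033 is called not significant under the present rule but could be called significant under Holm, with the same familywise guarantee. The effect of the block is not at stake here.

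**Working it through.** **Inputs**
- Assessment times: k = 6 (PACU, and 1, 6, 12, 24 and 48 hours on the ward), from the Methods.
- Overall level: 0.05, from the Statistical Analysis paragraph. Sidedness is not stated; two-sided is assumed.
- Stated corrected level: 0.0033, same paragraph.
- Patients: 30 per group, 60 in total, from Design and Subjects.
- VAS means, SDs and correlations between times: not given, so assumed below.

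**1. Reproducing the plan's figure**

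Pairs among six times: m = 6 × 5 / 2 = 15. Bonferroni level: 0.05/15 = 0.00333, which rounds to the stated 0.0033. Other readings do not fit:
- 0.05/14 = 0.0036
- 0.05/16 = 0.0031
- 0.05/30 = 0.0017 (15 pairs in each of two groups, counted as one family)
- 0.05/6 = 0.0083 (one between-group test per time)
- Šidák with 15 tests: 1 − 0.95^(1/15) = 0.0034

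The level therefore corresponds to one set of 15 time pairs.

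**2. Holm's thresholds**

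Order the p values from smallest to largest and compare the i-th with 0.05/(15 − i + 1), stopping at the first failure:

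0.0033, 0.0036, 0.0038, 0.0042, 0.0045, 0.0050, 0.0056, 0.0063, 0.0071, 0.0083, 0.0100, 0.0125, 0.0167, 0.0250, 0.0500.

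The first equals the Bonferroni level and every later one is larger. Two things follow without simulation. Every pair that Bonferroni rejects is also rejected by Holm. Results differ only if some p value lies between 0.0033 and its own step threshold, with all smaller p values already rejected. If ten pairs have been rejected, for example, the eleventh is judged at 0.05/5 = 0.0100, about three times the fixed level.

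**3. Size of the gain (simulation)**

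Assumptions: n = 30, six normally distributed scores with equal correlation ρ, linear fall from first to last time, Wilcoxon signed-rank tests by normal approximation, 10,000 datasets per scenario.

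| Total fall (SD) | ρ | Mean pairs found, Bonferroni | Mean pairs found, Holm | Datasets where Holm finds more |
|---|---|---|---|---|
| 0.5 | 0.3 | 0.53 | 0.56 | 2.6% |
| 0.5 | 0.5 | 0.89 | 0.95 | 4.6% |
| 1.0 | 0.5 | 4.71 | 5.22 | 38.2% |
| 1.5 | 0.5 | 8.00 | 8.94 | 60.8% |
| 2.0 | 0.5 | 10.00 | 11.22 | 71.1% |
| 2.0 | 0.7 | 11.52 | 13.10 | 79.1% |

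Across the scenarios with a steady fall, the mean gain runs from 0.56 − 0.53 = 0.03 pairs to 13.10 − 11.52 = 1.58 pairs. Holm never found fewer. The chance of finding at least one pair was identical for both methods, as it must be, since the first threshold is the same.

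If all 60 patients form the analysis set, three assumed profiles with large falls (2.2 to 5 cm, SD 2 cm, ρ = 0.5) gave 8.6 to 13.6 pairs with Bonferroni and 9.4 to 14.7 with Holm, with at least one more pair in 58% to 74% of datasets. Weak falls were not examined at that size, so this range leans towards a large gain.

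**4. Error control**

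Holm's 5% bound is a theorem that holds under any dependence, which matters because the scores are repeated measures. Scenarios in which all 15 pairs truly differ cannot show the error rate, so null scenarios were run separately (n = 30, ρ = 0.3 to 0.7). With no true differences, familywise error was 0.031 to 0.032 for both methods. With some true and some null pairs, it was 0.006 to 0.023 for Bonferroni and 0.013 to 0.027 for Holm. All are below 0.05.

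**5. The family**

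If the 15 pairs are tested in each group, there are 30 tests. The stated level then bounds the error at 15 × 0.0033 = 0.0495 per group and 30 × 0.0033 = 0.099 over both. Holm applied per group inherits the same feature.

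**The case against.** The strongest reply is that nothing is wrong. Single-step Bonferroni is valid and correctly computed here, and choosing between valid familywise methods may look like taste. By the same logic Holm could be faulted, since Shaffer's procedure for all-pairwise families is at least as powerful. The validity point stands in full. The taste point does not quite: Holm needs no extra assumption and no new computation, and it can never do worse on rejections. Shaffer's procedure relies on logical relations between the hypotheses, which paired Wilcoxon nulls do not automatically satisfy. Single-step Bonferroni has the advantage of simple simultaneous intervals, but none are planned.

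Second, the stated objective is the effect of the block, which is a comparison of groups, and contrasts between times do not estimate it. This stands, and it is why the point is minor. The time pairs are nevertheless a stated analysis with their own stated threshold.

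Third, the study ended in July 2018, so a switch now is a change after completion that can only add significant results. That is true and calls for disclosure. The error bound survives, because Bonferroni's rejections are always a subset of Holm's: choosing between these two after seeing the data cannot reject more than Holm alone.

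A reader might infer three stronger things, none of which the documents support. One is that 0.0033 is a mistake; it reproduces exactly. Another is that real changes in pain have been missed; the documents report no VAS results, so one can say only that some may be. The third is that the conclusion about the block could change; those tests do not use this threshold.

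**Conclusion.** The point holds as an improvement in efficiency, not as an error. On the within-patient time comparisons, Holm gives the same 5% familywise control and at least as many rejections. The gain ranges from negligible when pain falls little to between one and two of 15 pairs on average when it falls strongly, and in a given dataset it may be nil. The dominance of Holm over Bonferroni rests on no assumption. The size of the gain rests entirely on the assumed means, SD, correlations and normal scores. The count of 15 is inferred from the six times and the stated level. Severity is low: a free improvement.

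**What to change.** Replace the fixed threshold with a sentence such as:

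> Paired Wilcoxon p values are adjusted by Holm's step-down method over the 15 time pairs within each analysed set of patients [state: each group separately, or all 60 patients]; adjusted p<0.05 is significant.

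Naming the analysis set matters, because the 5% control applies to that family only. State in the report that the change was made after completion; giving the Bonferroni results alongside would let readers see what it altered.

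The cost is one sentence and a re-sorting of 15 existing p values per set. No further data or tests are needed, error control is unchanged, and the Hypo versus No-Hypo tests stay as they are. The remaining cost is the disclosed departure from the stated rule.
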